# St. George's Respiratory Questionnaire

	ctivities that your respiratory problems may prevent you from these, they are just to remind you of ways your shortness of i	
Going for walks or	walking the dog	
Doing activities or o	chores at home or in the garden	
Sexual intercourse		
Going to a place of	worship, or a place of entertainment	
Going out in bad we	eather or into smoky rooms	
Visiting family or fri	ends or playing with children	
Please write in any	other important activities that your respiratory problems may stop	o you from
doing:		
		***
Now please check affect you:	the box (one only) that you think best describes how your respira	tory problems
	It does not stop me from doing anything I would like to do	
	It stops me from doing one or two things I would like to do	
	It stops me from doing most of the things I would like to do	
	It stops me from doing everything I would like to do	
Thank you for completing answered all the question	g this questionnaire. Before you finish would you please make suns.	ire that you hav

USA / US English version

0

1.\institut\cultadap\project\gsk1001\guestion\inal versions\sgrausaq.doc 18/04/03

# 15.4 UNIVERSITY OF CALIFORNIA SAN DIEGO SHORTNESS OF BREATH QUESTIONNAIRE (EXAMPLE)

# UCSD MEDICAL CENTER PULMONARY REHABILITATION PROGRAM SHORTNESS-OF-BREATH QUESTIONNAIRE

© 1995 The Regents of the University of California

Please rate the breathlessness you experience when you do, or if you were to do, each of the following tasks. **Do not skip any items**. If you've never performed a task or no longer perform it, give your best estimate of the breathlessness you would experience while doing that activity. Please review the two sample questions below before turning the page to begin the questionnaire.

When I do, or if I were to do, the following tasks, I would rate my breathlessness as:

0 1	1	
2 3 4	3	
4	4 Severe	
5		
1.	Brushing teeth 0 1 2 3 4	5
	arry has felt moderately short of breath during the past week while brushing his to r this activity.	eth and so circles a three
2.	Mowing the lawn 0 1 2 3 4	©

Anne has never mowed the lawn before but estimates that she would have been too breathless to do this activity during the past week. She circles a five for this activity.

# When I do, or if I were to do, the following tasks, I would rate my breathlessness as:

0 1 2 3	None at all						
4 5	Severe Maximal or unable to do because of breathlessness						
1.	At rest0	1	2	3	4	5	
2.	Walking on a level at your own pace0	1	2	3	4	5	
3.	Walking on a level with others your age0	1	2	3	4	5	
4.	Walking up a hill0	1	2	3	4	5	
5	Walking up stairs0	1	2	3	4	5	
6.	While eating0	1	2	3	4	5	
7.	Standing up from a chair0	1	2	3	4	5	
8.	Brushing teeth0	1	2	3	4	5	
9.	Shaving and/or brushing hair0	1	2	3	4	5	
10.	Showering/bathing0	1	2	3	4	5	
11.	Dressing0	1	2	3	4	5	
12.	Picking up and straightening0	1	2	3	4	5	

When I do, or if I were to do, the following tasks, I would rate my breathlessness as:

0 1 2	None at all						
3 4 5	Severe Maximal or unable to do because of breathlessness						
13	Doing dishes 0		2	3	4	5	
	Sweeping /vacuuming				4	5	
	Making bed0		2		4	5	
16.	Shopping0	1	2	3	4	5	
17.	Doing laundry0	1	2	3	4	5	
18.	Washing car0	1	2	3	4	5	
19.	Mowing lawn0	1	2	3	4	5	
20.	Watering lawn0	1	2	3	4	5	
21.	Sexual activities0	1	2	3	4	5	
Но	w much do these limit you in your daily life?						
22.	Shortness of breath0	1	2	3	4	5	
23.	Fear of "hurting myself" by overexerting0	1	2	3	4	5	
24.	Fear of shortness of breath0	1	2	3	4	5	

# 15.5 PATIENT GLOBAL ASSESSMENT (EXAMPLE)

**Question 1:** "Over the past week, on average, how many times has **fatigue** limited your ability to do what you wanted?"

- All of the time
- Several times per day
- At least once a day
- 3 or more times per week, but not every day
- 1-2 times per week
- Less than once a week
- Never over the past week

**Question 2:** "Over the past week, on average, how many times has **shortness of breath** limited your ability to do what you wanted?"

- All of the time
- Several times per day
- At least once a day
- 3 or more times per week, but not every day
- 1-2 times per week
- Less than once a week
- Never over the past week

### 15.6 GUIDELINES AND DEFINITIONS FOR RECORDING ADVERSE EVENTS

The Investigator or a designated member of their staff will probe each subject for any AEs that may have occurred. The Investigator should always ask the same question when conducting the verbal probe in order to ensure uniformity between subjects. The Investigator should ask:

"How are you doing (feeling)?"

Based on the subject's response to this question, the Investigator should ask additional questions relevant to the specific complaint such as:

"How severe is/was the symptom?"

"How often did the symptom occur?"

"How long did the symptom last?"

It is the Investigator's responsibility to review the results of all diagnostic and laboratory tests as they become available and ascertain if there is a clinically significant change from baseline. If the results are determined to be a clinically significant change from baseline, this should be reported as an AE. The Investigator may repeat the diagnostic procedure or laboratory test or request additional tests to verify the results of the original tests. When possible, a diagnosis associated with the abnormality should be used as the reported AE.

Using provided definitions, the Investigator will then:

(1) rate the intensity and seriousness of the AE, (2) estimate the causality of the AE to study drug, and (3) note actions taken to counteract the AE.

Definitions of Intensity, Seriousness, Causality, Action Taken, and Outcome

#### **INTENSITY**

An assessment of the relative intensity (severity) of an AE is based on the Investigator's clinical judgment. The maximum intensity encountered during the evaluation period should be checked. The assessment of intensity should be independent of the assessment of the seriousness of the AE.

- Mild: Discomfort noticed, but no disruption to daily activity
- Moderate: Discomfort sufficient to disrupt normal daily activity
- Severe: Inability to work or perform normal daily activity

#### **SERIOUSNESS**

An SAE is one that represents an actual or potential significant hazard. This includes, but is not limited to, an event that is fatal, life-threatening, permanently or severely disabling, requires or prolongs inpatient hospitalizationa, is a congenital abnormality (offspring of subject) or is medically significant (important medical events that may not result in death, be life-threatening, or require hospitalization may be considered an SAE when, based upon appropriate medical judgment, they may jeopardize the subject and may require medical or surgical intervention to prevent 1 of the outcomes listed in this definition).

- a Hospitalizations that would not be considered SAEs include those for:
  - Routine treatment or monitoring of the study indication not associated with any deterioration in condition (eg, hospitalization for a routine RHC).
  - Treatment that was elective or pre-planned for a pre-existing condition and not associated with any deterioration in condition (eg, pre-planned operation which does not lead to further complications etc).
  - Treatment of an emergency, in an outpatient setting for an event not fulfilling any of the definitions of serious as given above and not resulting in hospital admission.

#### **CAUSALITY**

An estimate of causality between a specified AE and the study drug is made by the Investigator. Several factors should be considered when determining causality. These factors include temporal relationship and response to withdrawal or reintroduction of the study drug.

Definitions of the causality categories are as follows:

- NOT RELATED There is not a temporal relationship to study drug administration (too early, or late, or study drug not taken), or there is a reasonable causal relationship between another drug, or concurrent disease and the SAE, or any of the following:
  - An event that precedes the first administration of study drug
  - An event for which the cause is clearly related to an external event
  - Temporal relationship to study drug is atypical
  - Is readily explained by an intercurrent illness AND has an expected level of severity, duration, and resolution
  - An alternative explanation (concomitant drug, intercurrent illness) is likely
- POSSIBLE There is a reasonable causal relationship between the study drug and the SAE. Dechallenge information is lacking or unclear, study drug administration was not modified in response to the SAE, or any of the following:

- Has a reasonable temporal relationship to study drug
- The event has a plausible biological link to the activity of the study drug
- Is unlikely to be related to an intercurrent illness or has an unexpected degree of severity, duration, or complication
- PROBABLE There is a reasonable causal relationship between the study drug and the SAE. The event responds to dechallenge the event resolves or improves with modification of study drug administration. Rechallenge (the original study drug was restarted) is not required, or any of the following:
  - Has a reasonable temporal relationship to study drug
  - The event has a plausible biologic link to the activity of the study drug
  - Not readily explained by an intercurrent illness
  - Not readily explained by external event
  - Improves on discontinuation of study drug
  - If study drug has been discontinued, may recur or reintroduction of study drug

#### **ACTION TAKEN**

### STUDY DRUG DOSE MODIFICATION

- Dose Not Changed The dose or regimen of the study drug was not changed
- Dose Increased The dose or regimen of study drug was increased
- Dose Decreased The dose or regimen of study drug was decreased
- Drug Interrupted Administration of the study drug was stopped temporarily
- Drug Withdrawn Administration of the study drug was stopped permanently and not restarted
- Unknown Changes to the administration of the study drug cannot be determined
- Not Applicable (only used if the AE was started and resolved prior to Tyvaso dosing used in the study treatment periods, or for an AE that started after permanent discontinuation from study treatment)

NOTE: Only the last study drug action should be recorded in the eCRF. For example, if the study drug is withdrawn and then the decision is made to restart, the dose modification of "Drug interrupted" should be reported on the SAE form.

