#### **Drug Dosage and Formulation:**

- Active Study Drug: Inhaled treprostinil solution (0.6 mg/mL, 6 mcg/breath), 4 times daily (QID) during waking hours.
- Placebo Study Drug: Placebo inhalation solution, QID during waking hours.

All subjects will be given low dose inhaled treprostinil during the Screening Period. After randomization, study drug will be initiated based on randomized treatment assignment and dose adjustments will be based on subject tolerability at the discretion of the Investigator. Study drug doses should be maximized to tolerability throughout the study and dose escalations (additional 1 breath QID) can occur approximately every 3 days with a target dosing regimen of 12 breaths QID or the maximum tolerated dose.

Control Group: Placebo

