# 6 DRUGS AND DOSING (OR TREATMENT PROCEDURES)

#### 6.1 DRUG DOSAGE, ADMINISTRATION AND SCHEDULE

Treprostinil for inhalation solution (0.6 mg/mL) is delivered via the Tyvaso Inhalation System, which emits a dose of approximately 6 mcg per breath. Placebo will be provided as an identical solution for inhalation using the same Tyvaso Inhalation System. Subjects will receive study drug (inhaled treprostinil or placebo) via the Tyvaso Inhalation System and will be trained on use of the Tyvaso Inhalation System at Screening Visit 1. In addition, subjects will receive a copy of the Tyvaso Inhalation System Instructions for Use. The first dose of study drug (3 breaths, 18 mcg) will be inhaled at the study site, followed by at least a 1-hour observation period.

Once informed consent has been signed, all entry criteria have been met (including Sponsor Medical Monitor Approval), and the randomized treatment assignment confirmed, study drug doses should be maximized throughout the study and dose escalations (additional 1 breath QID) can occur approximately every 3 days with a target dosing regimen of 12 breaths (72 mcg) QID

or the maximum tolerated dose. Table 6-1 provides an example of dose escalations that can be followed.

**Table 6-1** Sample Inhaled Treprostinil Dose Escalation Table

Study Day a	Single Dose	Total Daily Dose	
Titrating to maximum dose of 12 breaths			
1 to 3	3 breaths QID (18 mcg)	72 mcg	
4 to 6	4 breaths QID (24 mcg)	96 mcg	
7 to 9	5 breaths QID (30 mcg)	120 mcg	
10 to 12	6 breaths QID (36 mcg)	144 mcg	
13 to 15	7 breaths QID (42 mcg)	168 mcg	
16 to 18	8 breaths QID (48 mcg)	192 mcg	
19 to 21	9 breaths QID (54 mcg)	216 mcg	
22 to 24	10 breaths QID (60 mcg)	240 mcg	
25 to 27	11 breaths QID (66 mcg)	264 mcg	
28 (and beyond)	12 breaths QID (72 mcg)	288 mcg	

QID, 4 times daily

The above dosing schedule is recommended as a guide only. The Investigator may accelerate or decelerate the dosing titration schedule on an individual subject basis, considering subject safety, tolerability, and functional improvement.

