10.2.5 Summary of Treatment Emergent Adverse Events

An overall summary of AEs by treatment received at the time of the event and treatment will contain the following:

- Total number of AEs, total number of subjects with at least one AE
- Total number of related AEs, total number of subjects with at least one related AE
- Total number of serious adverse events (SAEs), total number of subjects with at least one SAE
- Total number of AEs leading to study withdrawal
- Total number of AEs leading to treatment discontinuation.

Table summaries of all AEs will present numbers and percentages by SOC and PT of the following by treatment received at the time of the event:

- Subjects with at least one AE
- Subjects with at least one treatment-related AE
- Subjects with at least one SAE
- Subjects with an AE leading to treatment discontinuation.

AEs will also be summarized by treatment received at the time of the event for the following:

- AEs by severity
- AEs by relationship to treatment
- AEs by action taken with treatment, separately
- Listing of all SAEs.

Finally, a table summarizing the AEs that occurred during the pre-randomization run-in phase will be presented for all screened subjects.

Adverse events will be presented in alphabetical order of SOC and by decreasing order of incidence of the PTs.

For these summaries, a subject having the same AE multiple times will only be counted once for the corresponding PT. Similarly, a subject who experienced multiple AEs within the same SOC will be counted only once for that SOC.

A subject experiencing the same AE multiple times or at multiple severities will only be counted once under that PT at the worst severity rating. Similarly, a subject who experiences the same AE multiple times or at multiple severities across multiple PTs within the same SOC will only be counted once for the worst severity rating within the SOC.

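### Keeping only the last study drug action per adverse event can hide dose reductions that were later reversed, and 'Not Applicable' can be read to cover run-in events for which treprostinil was reduced or stopped

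*Protocol*

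**What the plan says.** Protocol Appendix 15.6, under Action Taken, lists seven categories: dose not changed, increased or decreased, drug interrupted or withdrawn, unknown, and not applicable. The note below them says "NOTE: Only the last study drug action should be recorded in the eCRF". Its one example is that "if the study drug is withdrawn and then the decision is made to restart, the dose modification of 'Drug interrupted' should be reported", and there it refers to the SAE form, not the eCRF. *Drug Withdrawn* is defined as a permanent stop and *Drug Interrupted* as a temporary one. Earlier in the appendix the Investigator is asked to "note actions taken to counteract the AE".

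The first part of *Not Applicable* is "only used if the AE was started and resolved prior to Tyvaso dosing used in the study treatment periods". Its second part covers AEs that begin after permanent discontinuation.

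SAP 10.2.3 gives each AE one of the same seven values. SAP 10.2.5 lists "AEs by action taken with treatment, separately" among the planned summaries.

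On dosing, the protocol synopsis says "Study drug doses should be maximized to tolerability throughout the study and dose escalations (additional 1 breath QID) can occur approximately every 3 days". Protocol 6.1 repeats the instruction and adds "The Investigator may accelerate or decelerate the dosing titration schedule on an individual subject basis".

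**The concern.** In a trial that titrates to tolerability, a dose-limiting symptom may be handled by lowering the dose and raising it again later. No category means reduced and then restored, and a rule that keeps only the last step can erase the reduction. The table of AEs by action taken would then show a poorly tolerated event as a dose increase.

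Tolerability events are likely to be common. Protocol 1.2.3 reports cough in 54%, headache in 41% and nausea in 19% of the inhaled treprostinil group in the earlier Phase 3 trial in pulmonary arterial hypertension. Appendix 15.6 also rests a *Probable* causality rating partly on improvement after study drug was modified. If the modification is overwritten, such an AE could be listed as *Probable* next to *Dose Increased*, and a reader could not reconcile the two.

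The *Not Applicable* wording raises a separate question: what happens to actions taken on treprostinil before randomization.

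**Working it through.** The plan states no figure that depends on this rule, so the check is mainly a comparison of texts.

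**1. What the note does to each course.** The two coding columns come from the note and category definitions (literal reading) and from the request to record what counteracted the AE (purpose reading).

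| Course for one AE | Literal last action | Purpose reading |
|---|---|---|
| Reduced, then raised while the AE is open | Dose Increased | Dose Decreased |
| Reduced, AE resolves, then raised | Dose Decreased, if the AE is treated as closed | Dose Decreased |
| Held, then restarted at the same dose | Drug Interrupted (the note's example) | Drug Interrupted |
| Held, then restarted at a lower dose | Dose Decreased | Drug Interrupted |
| Stopped for good | Drug Withdrawn | Drug Withdrawn |

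The readings part in the first and fourth rows. Two sites could code the same course differently and each point to the appendix.

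**2. Whether another planned summary recovers the loss.**

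- The primary reason for withdrawal (Protocol 8.1.1) and the discontinuation tables (SAP 10.2.5) capture permanent stops only.
- Telephone contacts go into the eCRF (Protocol 3.3.2.12), but no analysis of reductions is planned from them.
- SAP 10.1 summarizes maintenance dose as the mode over the treatment period. In the sample schedule (Protocol Table 6-1), going from 3 to 12 breaths takes 12 − 3 = 9 steps of 3 days, so 12 breaths starts on day 28. Days 28 to 84 are 84 − 28 + 1 = 57 days. Suppose one cut to 11 breaths lasts d days before return to 12. Days at 12 breaths are 57 − d. Days at 11 breaths are 3 + d, because days 25 to 27 are also at 11. The mode stays at 12 while 57 − d > 3 + d, that is d < 27. At d = 26 it is 31 days against 29. Under that guide-only schedule, a one-breath cut of up to 26 days leaves the modal dose unchanged.

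No planned summary counts reductions apart from the action-taken table.

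**3. The run-in.** *Not Applicable* turns on dosing in the study treatment periods. An AE that starts and resolves during the 14 to 18 day open-label run-in fits that wording even if treprostinil was reduced or stopped. SAP 7.1 sets the safety baseline before the first run-in dose, and SAP 10.2 provides for low-dose treprostinil and any-treprostinil AE tabulations. Both treat the run-in as exposure. Protocol 3.6 also counts it within the 26 weeks of treatment, so the phrase is open to more than one reading.

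**4. Size.** Let f be the share of AE-driven reductions that are reversed while the AE is open and coded literally. Then reductions shown = true reductions × (1 − f). The documents give neither the reduction rate nor f. Purely as an illustration, take the 136 subjects planned for the crossover and assume 10% to 40% have such a reduction:

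- True number: 136 × 0.10 = 13.6 to 136 × 0.40 = 54.4.
- Shown at f = 0: 13.6 to 54.4. At f = 50%: 6.8 to 27.2. At f = 100%: none.

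This counts subjects, whereas the planned item counts AEs. The range runs from no loss to total loss, so it describes the mechanism and does not estimate the effect.

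**The case against.** The strongest reply is that the field is for actions that counteract the AE. Raising the dose after symptoms settle is ordinary titration, and the AE may already be closed by then. On that reading the decrease is kept and nothing is lost. This stands far enough that the point must be *can be coded*, not *is coded*. It does not remove the problem, because the note itself says last action without that limit. The eCRF completion guidelines mentioned in Protocol 10.1 may settle the coding, but they are not among the documents.

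A reader might infer several stronger things that the documents do not support:

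- *That the note's example contradicts its rule.* It does not. A restart is not a category, and once drug is restarted, *Drug Interrupted* is the correct final classification. The example keeps a reversed stop visible.
- *That the protocol orders re-escalation after an AE.* It asks for maximization to tolerability, with titration at the Investigator's discretion.
- *That the table will narrow the active-placebo difference.* This needs reductions to be commoner on active drug and the loss to be similar in both arms. With assumed rates of 20% and 5% (true difference 15 points), f = 50% in both arms shows 10 − 2.5 = 7.5 points. With f = 0 on active and 100% on placebo it shows 20 − 0 = 20 points. The direction depends on the assumptions.
- *That run-in coding biases the randomized comparison.* The run-in has no placebo arm, and subjects intolerant in it are screen failures. Their AEs have a separate table in SAP 10.2.5, although action taken is not named as part of it.

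It is also fair that no inferential AE analysis is planned, and that the severity, relatedness and discontinuation summaries do not use this note.

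**Conclusion.** The point holds in a limited form. A stated recording rule can lose safety information, chiefly AE-driven dose reductions reversed while the AE is open, and also interruptions followed by restart at a lower dose. The planned action-taken table is the only AE-level summary that would show them. Inconsistent coding between sites is likely enough to deserve a clear rule. Neither the size nor the direction of the effect on the treatment comparison can be computed from the documents.

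The *Not Applicable* wording is a separate and smaller matter. On its plain reading it sits badly with the SAP's treatment of the run-in as exposure, and it affects only how low-dose tolerability is described.

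Neither point touches the primary endpoint, the sample size or the Type I error rate. This is a low-cost improvement to safety recording, not a threat to the trial's main conclusion.

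**What to change.** Replace the note in Appendix 15.6 with wording such as: *Record the most restrictive action taken in response to that AE: Drug Withdrawn (only if stopped permanently and not restarted), then Drug Interrupted (including stopped and later restarted), then Dose Decreased, then Dose Increased only if the increase was itself made in response to the AE, then Dose Not Changed. Use Unknown only if the action cannot be determined. Later re-escalation is recorded only in the dosing record.* State that it applies to all AEs, on both the eCRF and the SAE form.

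Redefine the pre-dosing part of *Not Applicable* as AEs that started and resolved before the first dose of any study drug, including the run-in. Leave the part on AEs after permanent discontinuation as it is.

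The seven categories and SAP 10.2.3 and 10.2.5 need no change, and no dose or clinical rule is affected. The cost is a short clarification to sites and queries on entries already made. One limit remains: with a single value per AE, a hold followed by restart at a lower dose would show as an interruption, and the reduction would appear only in the dosing record.
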